9.7. Concomitant Medication

Prior and concomitant medications will be summarized descriptively by treatment, Anatomical Therapeutic Chemical (ATC) Class Level 4, and Preferred Term using counts and percentages.

Prior medications will be presented separately from concomitant medications. Medications that started before the first application of IP will be considered prior medications whether or not they were stopped prior to the first application of study drug. Any medications continuing or starting after the first application of study drug will be considered to be concomitant. If a medication starts before the first application of study drug and continues after the first application of study drug it will be considered both prior and concomitant.

Medications will be coded using World Health Organization (WHO) Drug Global B3, version March 2022.

9.8. Physical Examination

The number and percentage of subjects with normal and abnormal findings in the physical examination will be displayed at each study visit and treatment group.

10. OTHER PLANNED ANALYSIS

10.1. Pharmacokinetic Analysis

All PK collection information from the eCRF, along with PK concentrations, will be presented in a listing. Concentration data will be summarized by study visit and treatment group using summary statistics. Sample values reported below the limit of quantification (BLQ) will be set equal to zero for plasma descriptive statistics. The lower limit of quantification (LLOQ) is 0.100 ng/mL for roflumilast and the N-oxide metabolite. For the analysis of the pre-dose plasma concentrations only, to allow for the calculation of geometric mean, 0.0001 will be added to all concentration values to remove all zero values. Addition of 0.0001 will only be necessary if there are 1 or more values BLQ.

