3.7. Schedule of Events

A detailed schedule of events for the study is provided in [Table 1](#).

Table 1: Schedule of Events

| Study Procedure | Screening | Baseline Day 1 | Week 2 Day 15 | Week 4 Day 29 | Week 8 ^a Day 57 |
|--|-----------|-------------------|-----------------------|------------------|-------------------------------|
| Visit | 1 | 2 | 3 | 4 | 5 |
| Visit Window | -4 Weeks | | ± 3 Days | ± 5 Days | ± 5 Days |
| Informed consent/assent | X | | | | |
| Medical/surgical history, demography | X | | | | |
| Physical examination ^b | X | X | | | X |
| Fitzpatrick Skin Type | X | | | | |
| I/E criteria | X | X | | | |
| Randomization | | X | | | |
| Hematology, Chemistry, and Urinalysis ^c | X | X | | X | X |
| Vital signs, weight, height ^d | X | X | X | X | X |
| S-IGA ^e , B-IGA ^e , PSSI ^e , BSA ^f , Extent of Scalp Involvement ^g , PASI | X | X | X | X | X |
| DLQI/CDLQI ^h , Scalpdex ^h , PSD ^h | X | X | X | X | X |
| Daily SI-NRS and WI-NRS ⁱ at home (non-clinic) | | | Day -7 through Day 57 | | |
| Application Site Reaction Assessment/ Local Tolerability ^j | | X | X | X | X |
| C-SSRS, PHQ-8/PHQ-A ^k | X | X | | X | X |
| Medical Photography ^l | | X | X | X | X |
| Follicle Stimulating Hormone (FSH) ^m | X | | | | |
| Serum pregnancy test ^m | X | | | | |
| Urine pregnancy test ⁿ | | X | | X | X |
| PK sampling ^o | | | | X | X |
| IP application and subject/family training ^p | | X | X | X | |
| Dispense investigational product kit ^q | | X | X | X | |
| Dispense / review dosing diary | | X | X | X | X |
| Weigh investigational product ^r | | X | X | X | X |
| Compliance calculation ^s | | | X | X | X |
| Adverse event assessment ^t | X | X | X | X | X |
| Concomitant medications | X | X | X | X | X |

Footnotes from table above:

- a. Subjects that terminate early should return to the study site for the Week 8 assessments.
- b. Limited physical examination: skin (including assessment of Fitzpatrick Skin Type at Screening only), lungs, and heart only.
- c. For subjects <18 years of age, if the Baseline/Day 1 visit occurs within 3 weeks of Screening, the Screening lab results may be utilized.

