Note for Investigator tolerability assessments: reactions at the site of IP application, which may occur post-Baseline, should be differentiated from the preexisting inflammation associated with the subject's psoriasis. The subject's "0-3" burning/stinging assessment is to be recorded 10-15 minutes post IP application for the subject's "0-3" burning/stinging assessment. **At Week 8, subjects will provide a recall assessment of burning/stinging experienced post IP application on the day prior to the clinic visit.**
- k. All subjects will complete the C-SSRS. Adults will complete the PHQ-8. Adolescents (ages 12 to 17 inclusive) will complete the PHQ-A (PHQ-9 modified). Refer screen failures due to score ≥ 10 to a mental health professional. For Scores 10-14 at all visits, refer subject promptly to a mental health professional. For scores ≥ 15 at all visits, refer subject promptly to a mental health professional and consider interruption of IP.
- l. Medical photography will be obtained for target lesions by all sites. All efforts will be made to de-identify the subjects.
- m. A serum pregnancy test will be administered to all females of child-bearing potential at the Screening visit only. Follicle Stimulating Hormone (FSH) will be performed at Screening (if indicated) to confirm post-menopausal status.
- n. A urine pregnancy test will be performed at the Baseline, and Weeks 4 and 8 to all females of child-bearing potential. A negative result is required for continued participation in the study, and results must be available at each visit prior to dispensing of IP.
- o. PK samples (trough) will be collected predose on Day 29 (Week 4) and Day 57 (Week 8). Ensure investigational product is not applied in the area where PK will be drawn.
- p. Subjects/parents/caregivers to apply assigned IP in the study site at every designated visit.
- q. Kits will be dispensed based on % BSA. See IP Handling Plan for details.
- r. Each IP canister in the Kit should be weighed and recorded at every visit. See IP Handling Plan for details.
- s. Compliance calculation is described [Section 6.1.7](#) and in the IP Handling Plan.

Footnote from table above:

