4. STATISTICAL ANALYSIS AND REPORTING

4.1. Introduction

Data processing, tabulation of descriptive statistics, calculation of inferential statistics, and graphical representations, will be performed primarily using SAS (release 9.4 or higher). If the use of other software is warranted for analyses conducted by Premier Research, the final statistical methodology report will detail what software was used for what purposes.

Continuous (quantitative) variable summaries will include the number of subjects (n) with nonmissing values, mean, standard deviation (SD), median, minimum, maximum, first quartile (Q1), and third quartile (Q3).

Categorical (qualitative) variable summaries will include the frequency and percentage of subjects who are in the particular category or each possible value. In general, the denominator for the percentage calculation will be based upon the total number of subjects in the study population for the treatment group, unless otherwise specified.

Unless otherwise indicated, all statistical tests will be conducted at the familywise $\alpha=0.025$ significance level using 2-tailed tests, and P values will be reported. Corresponding 95% and 97.5% confidence intervals will be presented for statistical tests. Details for splitting the familywise α to control for multiple comparisons will be discussed in [Section 6.1.3](#).

All data collected in the electronic case report form (eCRF) will be provided in subject listings.

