5. ANALYSIS POPULATIONS

The following analysis populations are planned for this study:

- **Safety Population (SAF):** The Safety population will include all subjects who are randomized and received at least 1 confirmed dose of investigational product (IP). This population will be used for all safety analyses.
- **Intent-To-Treat Population (ITT):** The ITT population will include all randomized subjects. This population will be the primary analysis population for the analysis of efficacy endpoints, along with subject disposition.

- **Per Protocol (PP) Population:** The PP population will include the subjects in the ITT population who were at least 80% compliant with study drug application, have an S-IGA and B-IGA assessment at Week 8, and showed no important deviations from the study protocol that would affect the interpretation of efficacy. “Important deviations” will result from a blinded review at the end of the study and the team will determine the important deviations that can impact on efficacy. This population will be used for a supplemental analysis for primary efficacy endpoints.
- **Modified Intent-to-Treat Population (mITT):** The mITT population includes all randomized subjects with the exception of subjects who missed the Week 8 S-IGA or B-IGA assessment specifically due to COVID-19 disruption. This population will be used for sensitivity of the primary endpoints.
- **Scalp Pruritus ITT Population (SPRU4-ITT):** The SPRU4-ITT population is a subset of the ITT population and includes subjects with average weekly SI-NRS score ≥ 4 at baseline. This population will be used for the analysis of achievement of at least 4-point reduction in average weekly SI-NRS score as compared to baseline.
- **Pruritus ITT Population (PRU4-ITT):** The PRU4-ITT population is a subset of the ITT population and includes subjects with average weekly WI-NRS score ≥ 4 at baseline. This population will be used for the analysis of achievement of at least 4-point reduction in average weekly WI-NRS score as compared to baseline.
- **Pharmacokinetic Population (PK):** The PK population will include all subjects who received at least one confirmed dose of investigational product (IP) and provided at least one PK sample. This population will be used for summary of PK concentration results for subjects who applied roflumilast foam 0.3% during this study.

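### If any pre-dose PK sample is BLQ, the geometric mean in Table 14.4.1 depends on the added 0.0001 and on the BLQ share, so it needs the BLQ count and a sensitivity value beside it

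*SAP*

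**What the plan says.** SAP 10.1 summarises plasma concentrations by visit and treatment group, with BLQ samples entered as zero. "The lower limit of quantification (LLOQ) is 0.100 ng/mL for roflumilast and the N-oxide metabolite". For pre-dose concentrations only, and so that a geometric mean exists, "0.0001 will be added to all concentration values to remove all zero values". The step is conditional: "Addition of 0.0001 will only be necessary if there are 1 or more values BLQ". The section explains why some constant is added. It does not explain this value or print its unit.

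The rule reaches every scheduled PK sample, because SAP Table 1 (footnote o) has only troughs: "PK samples (trough) will be collected predose on Day 29 (Week 4) and Day 57 (Week 8"). Table 14.4.1 is the only planned PK table. The PK population is anyone who "received at least one confirmed dose of investigational product (IP) and provided at least one PK sample" (SAP 5), and its stated use is to summarise subjects who applied the active foam.

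SAP 4.1 defines the standard continuous summary as the count of "nonmissing values, mean, standard deviation (SD), median, minimum, maximum, first quartile" and third quartile. That list has no BLQ count. SAP 10.1 also says that the collection data, "along with PK concentrations, will be presented in a listing".

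**The concern.** A BLQ sample is known only to lie between 0 and 0.100 ng/mL. Adding 0.0001 looks negligible, and on the arithmetic scale it is. A geometric mean is an average of logs, however, and on that scale the choice places each BLQ sample 6.9 natural-log units below the LLOQ. A modest share of such samples can then pull the geometric mean well below the concentrations that were actually measured.

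At stake is how systemic exposure is read from the one PK table. The geometric mean could look lower than exposure really was. A difference in BLQ share between Week 4 and Week 8 could look like a larger change in exposure than occurred.

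**Working it through.** The SAP states no PK figure to reproduce, so the check is on how the rule behaves.

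**Inputs from SAP 10.1.** LLOQ = 0.1 ng/mL; constant c = 0.0001. **Assumed.** c is in ng/mL. The BLQ share f and the between-subject CV are in neither document, so ranges are shown.

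**Step 1: distance on the log scale.** LLOQ/c = 0.1/0.0001 = 1000, and ln(1000) = 6.91. By comparison, LLOQ/2 lies ln(2) = 0.69 below the LLOQ.

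**Step 2: dependence on the constant.** GM_plan = exp{(1 - f) E[ln(X + c) | X > 0.1] + f ln c}. The quantifiable values are hardly moved by c, so GM_plan is proportional to c^f, whatever the distribution of X. A tenfold change in c gives 10^f:

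- f = 5%: 1.12-fold
- f = 10%: 1.26-fold
- f = 20%: 1.58-fold

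**Step 3: comparison with LLOQ/2.** GM_alt = exp{(1 - f) E[ln X | X > 0.1] + f ln 0.05}. The ratio GM_alt/GM_plan is (0.05/0.0001)^f = 500^f: 1.02 for one BLQ sample in 280, 1.36 at 5%, 1.86 at 10% and 3.47 at 20%. It reaches 2 at f = ln 2/ln 500 = 11%.

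**Step 4: comparison with a true geometric mean.** Suppose all concentrations follow one lognormal distribution and the BLQ samples are its lower tail. Then s = sqrt(ln(1 + CV^2)), mu = ln 0.1 - s z_f, and E[ln X | X > 0.1] = mu + s phi(z_f)/(1 - f), where z_f is the f quantile of the standard normal.

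Worked case, CV 100% and f = 10%:

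- s = 0.833, z = -1.282, mu = -2.303 + 1.067 = -1.236, so the true GM is 0.291 ng/mL.
- The quantifiable log mean is -1.073.
- Plan: 0.9 x (-1.073) + 0.1 x ln(0.0001) = -0.966 - 0.921 = -1.887, so GM = 0.152. True/plan = 0.291/0.152, about 1.92.
- LLOQ/2: -0.966 + 0.1 x ln(0.05) = -0.966 - 0.300 = -1.266, so GM = 0.282.

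True GM divided by planned GM:

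| BLQ share | CV 70% | CV 100% | CV 150% |
|---|---|---|---|
| 1% | 1.07 | 1.07 | 1.07 |
| 5% | 1.39 | 1.39 | 1.38 |
| 10% | 1.94 | 1.92 | 1.90 |
| 20% | 3.71 | 3.63 | 3.53 |

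In this model LLOQ/2 stays within about 9% of the true value up to 30% BLQ. The planned geometric mean drops below the LLOQ once BLQ passes 11.5%, 13.9% or 16.6% (CV 70, 100, 150%), when more than 80% of samples are still quantifiable.

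**Step 5: change between visits.** In the same model, going from 10% to 20% BLQ is a true fall of 1.32-, 1.44- or 1.61-fold (CV 70, 100, 150%). Under the plan it reads as 2.53-, 2.73- or 3.00-fold.

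**Step 6: what is not affected.** With f = 0 the constant is not added. Below 50% BLQ the median is unchanged. With BLQ set to zero, the arithmetic mean at 20% BLQ is low by only 1.03- to 1.08-fold over CV 70-150%. The listing and all hypothesis tests are untouched.

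**The case against.** The strongest reply is that the harm is conditional. No BLQ share, CV or concentration level is documented. At 1% BLQ the effect is about 7%, and the 3.5-fold figures need 20% BLQ, which nothing in the documents supports or rules out. That stands: the size can be given only as a range.

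A reader might infer that the table would hide the problem. The documents do not support this. The SAP 4.1 summary includes minimum, first quartile and median. With BLQ entered as zero, a single BLQ sample prints a minimum below the LLOQ. What the minimum cannot show is the share of BLQ samples, which drives the distortion. Table shells and footnotes are not in the documents, so nothing more can be said about disclosure.

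A reader might also infer that LLOQ/2 is the right value and should replace the planned one for interpretation. Step 4 favours LLOQ/2 because it assumes that the BLQ samples are the lower tail of the exposed distribution. On the log scale 0.0001 is the closer value whenever BLQ samples truly lie below sqrt(0.0001 x 0.05) = 0.0022 ng/mL. If they were really 0.001 ng/mL at 10% BLQ, the plan would be low by (0.001/0.0001)^0.1 = 1.26-fold and LLOQ/2 high by (0.05/0.001)^0.1 = 1.48-fold. Such samples are possible: one dose and one sample qualify a subject for the PK population, and "Subjects that terminate early should return to the study site for the Week 8 assessments". The data were also unblinded on 12 September 2022 (SAP 1), so a substitution chosen now is post hoc. This objection stands and limits LLOQ/2 to a sensitivity role.

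Finally, SAP 10.1 summarises by treatment group. If a vehicle column is produced with all samples BLQ, LLOQ/2 would print 0.050 ng/mL for unexposed subjects. That stands too, so the added value belongs in the active arm only.

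**Conclusion.** The point holds and is minor. Whenever BLQ samples exist, the pre-dose geometric mean reflects the constant and the BLQ share as well as exposure. Step 2 needs no distributional assumption. The fold-errors of about 1.07 at 1% BLQ, 1.4 at 5%, 1.9 at 10% and 3.5-3.7 at 20% rest on three assumptions: the constant is in ng/mL, the BLQ samples are the lower tail of one lognormal distribution, and the CV is 70-150%.

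Two stronger readings are not supported. One is that the trial's PK results are distorted: the BLQ share is unknown, and with none BLQ there is no effect. The other is that 0.0001 has no rationale anywhere. The protocol lists PK sections (5.3.1, 6.1.7) whose text is not available in this copy, so the absence of a reason can be stated only for SAP 10.1. No endpoint, test, alpha level or power figure is involved.

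**What to change.** In Table 14.4.1, for each visit and analyte:

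- Report n and % BLQ.
- Keep the prespecified geometric mean, with a footnote that it depends on the 0.0001 constant and should be read with the median.
- For the roflumilast foam arm only, add a geometric mean with BLQ entered as LLOQ/2 (0.050 ng/mL) and nothing added to quantifiable values. Present it as a sensitivity value and label it post hoc, as SAP 1 requires of unplanned analyses.

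The other summaries keep BLQ = 0. The cost is a few extra rows and a footnote. LLOQ/2 is itself a convention, and it can overstate exposure if BLQ samples come from subjects who had stopped applying product.

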11. CHANGES FROM PLANNED ANALYSIS

11.1. Version 2.0

All the exploratory endpoints have been added in the SAP, but they were not specified in the protocol.

The following analysis populations have been added:

- The SPRU4-ITT population has been added to facilitate interpretation of the SI-NRS analysis in addition to the ITT population; and
- The PRU4-ITT population has been added to facilitate interpretation of the WI-NRS analysis in addition to the ITT population.

These populations are not discussed in the protocol.

In this SAP, PK population is defined as subjects who received at least one confirmed dose of investigational product (IP) and provided at least one PK sample. This population will be used for summary of PK concentration results. The definition is different from that in protocol where PK population is defined as subjects receiving active drug with sufficient plasma concentrations of roflumilast to define a profile, as determined by the pharmacokineticist, which will be used for analysis of PK parameters.

Version 2.0 of the SAP is based on the final version of Amendment 3 for the ARQ-154-309 protocol dated 29-Jul-2022. At the time of signing this SAP version 2.0, the protocol is approved and in the process of being published.

11.2. Version 3.0

Section 1 Overview provides a description of the rationale for SAP Version 3. The purpose of the SAP is to document the change to the primary estimand and related multiple imputation strategies. The revised estimand will be the focus of the Clinical Study Report and NDA. Key results based on the original estimand defined in SAP versions 1 and 2 will be provided as supplemental information for the primary and secondary endpoints covered by the multiple testing strategy. This change to the primary estimand and multiple imputation procedure was based on recommendations from FDA during a pre-NDA meeting for a similar program held on 14Sep2022.

14. TABLES, LISTINGS AND FIGURES

All listings, tables, and graphs will have a header showing the sponsor company name and protocol and a footer showing the version of SAS, the file name and path, and the source of the data (listing number).

14.1. Planned Table Descriptions

The following are planned summary tables for protocol number ARQ-154-309. The table numbers are place holders only and may be changed when the tables are produced.

| Table Number | Population | Table Title/Summary |
|------------------|-----------------------------|--|
| 14.1 | | Disposition, Baseline Characteristics and Exposure Summary |
| 14.1.1 | All Subjects | Subject Disposition |
| 14.1.2.1 | ITT | Demographics and Baseline Characteristics |
| 14.1.2.1 (cont.) | ITT | Demographics and Baseline Characteristics |
| | | |
| 14.1.2.1 (cont.) | ITT | Demographics and Baseline Characteristics |
| 14.1.2.1 (cont.) | ITT | Demographics and Baseline Characteristics |
| 14.1.2.1 (cont.) | ITT | Demographics and Baseline Characteristics |
| 14.1.2.1 (cont.) | ITT | Demographics and Baseline Characteristics |
| 14.1.2.2 | Safety | Demographics and Baseline Characteristics |
| 14.1.3 | Safety | Previous Treatment History of Scalp and Body Psoriasis |
| 14.1.4 | ITT | Protocol Deviations |
| 14.1.5 | Safety | Prior Medications by Anatomic Therapeutic Chemical (ATC) Class Level 4 and Preferred Term |
| 14.1.6 | Safety | Summary of Study Drug Exposure |
| 14.2 | | Efficacy Summary |
| 14.2.1 | ITT, SPRU4-ITT, or PRU4-ITT | Hypothesis Testing for Primary and Secondary Efficacy Endpoints - Multiple Imputation |
| 14.2.1.1 | ITT | Scalp Investigator Global Assessment (S-IGA) Grades and Success by Study Visit – Multiple Imputation (Primary Analysis) Categorical Results |
| 14.2.1.1.s | ITT | Scalp Investigator Global Assessment (S-IGA) Grades and Success by Study Visit – Multiple Imputation (Primary Analysis, Supplemental Estimand) Categorical Results |
| 14.2.1.2 | mITT | Scalp Investigator Global Assessment (S-IGA) Grades and Success by Study Visit – Multiple Imputation (Sensitivity Analysis) Categorical Results |
| 14.2.1.3 | ITT | Scalp Investigator Global Assessment (S-IGA) Grades and Success by Study Visit – Observed Data (Sensitivity Analysis) Categorical Results |
| 14.2.1.4 | Per-protocol | Scalp Investigator Global Assessment (S-IGA) Grades and Success by Study Visit – Observed Data (Supplemental Analysis) Categorical Results |
| 14.2.1.5 | ITT | Scalp Investigator Global Assessment (S-IGA) Grades and Success by Study Visit – Non-responder Imputation (Sensitivity Analysis) Categorical Results |
| 14.2.1.6 | ITT | Scalp Investigator Global Assessment (S-IGA) Grades and Success at Week 8 – Tipping Point Analysis (Sensitivity Analysis) Categorical Results |

| | | |
|-------------|-----|--|
| 14.2.1.7 | ITT | Scalp Investigator Global Assessment (S-IGA) Grades and Success by Study Visit – Multiple Imputation, without Site Stratification (Sensitivity Analysis) Categorical Results |
| 14.2.1.8.1 | ITT | Scalp Investigator Global Assessment (S-IGA) Success at Week 8 – Multiple Imputation, Impact of Site (Supporting Analysis) |
| 14.2.1.8.2 | ITT | Scalp Investigator Global Assessment (S-IGA) Success at Week 8 by Site – Observed Data (Supporting Analysis) |
| 14.2.1.9.1 | ITT | Scalp Investigator Global Assessment (S-IGA) Grades and Success by Study Visit and Response to Topical Corticosteroids – Multiple Imputation (Subgroup Analysis) |
| 14.2.1.9.2 | ITT | Scalp Investigator Global Assessment (S-IGA) Grades and Success by Study Visit and Age Group – Multiple Imputation (Subgroup Analysis) |
| 14.2.1.9.3 | ITT | Scalp Investigator Global Assessment (S-IGA) Grades and Success by Study Visit and Baseline S-IGA Disease Severity – Multiple Imputation (Subgroup Analysis) |
| 14.2.1.9.4 | ITT | Scalp Investigator Global Assessment (S-IGA) Grades and Success by Study Visit by Study Visit and Baseline B-IGA Disease Severity – Multiple Imputation (Subgroup Analysis) |
| 14.2.1.9.5 | ITT | Scalp Investigator Global Assessment (S-IGA) Grades and Success by Study Visit and Gender – Multiple Imputation (Subgroup Analysis) |
| 14.2.1.9.6 | ITT | Scalp Investigator Global Assessment (S-IGA) Grades and Success by Study Visit and Ethnicity – Multiple Imputation (Subgroup Analysis) |
| 14.2.1.9.7 | ITT | Scalp Investigator Global Assessment (S-IGA) Grades and Success by Study Visit and Race – Multiple Imputation (Subgroup Analysis) |
| 14.2.1.9.8 | ITT | Scalp Investigator Global Assessment (S-IGA) Grades and Success by Study Visit and Fitzpatrick Score – Multiple Imputation (Subgroup Analysis) |
| 14.2.1.9.9 | ITT | Scalp Investigator Global Assessment (S-IGA) Grades and Success by Study Visit and Facial Involvement – Multiple Imputation (Subgroup Analysis) |
| 14.2.1.9.10 | ITT | Scalp Investigator Global Assessment (S-IGA) Grades and Success by Study Visit and Genitalia Involvement – Multiple Imputation (Subgroup Analysis) |
| 14.2.1.9.11 | ITT | Scalp Investigator Global Assessment (S-IGA) Grades and Success by Study Visit and Knee Involvement – Multiple Imputation (Subgroup Analysis) |
| 14.2.1.9.12 | ITT | Scalp Investigator Global Assessment (S-IGA) Grades and Success by Study Visit and Elbow Involvement – Multiple Imputation (Subgroup Analysis) |
| 14.2.1.9.13 | ITT | Scalp Investigator Global Assessment (S-IGA) Grades and Success by Study Visit and Knee or Elbow Involvement – Multiple Imputation (Subgroup Analysis) |
| 14.2.1.9.14 | ITT | Scalp Investigator Global Assessment (S-IGA) Grades and Success by Study Visit and Response to Topical Vitamin D Derivatives – Multiple Imputation (Subgroup Analysis) |
| 14.2.1.10 | ITT | Summary, Change, and Percent Change from Baseline in Scalp Investigator Global Assessment (S-IGA) by Study Visit – Observed Data |
| 14.2.2.1 | ITT | Body Investigator Global Assessment (B-IGA) Grades and Success by Study Visit – Multiple Imputation (Primary Analysis) Categorical Results |
| 14.2.2.1.s | ITT | Body Investigator Global Assessment (B-IGA) Grades and Success by Study Visit – Multiple Imputation (Primary Analysis, Supplemental Estimand) Categorical Results |

| | | |
|-------------|--------------|---|
| 14.2.2.2 | mITT | Body Investigator Global Assessment (B-IGA) Grades and Success by Study Visit – Multiple Imputation (Sensitivity Analysis) Categorical Results |
| 14.2.2.3 | ITT | Body Investigator Global Assessment (B-IGA) Grades and Success by Study Visit – Observed Data(Sensitivity Analysis) Categorical Results |
| 14.2.2.4 | Per-Protocol | Body Investigator Global Assessment (B-IGA) Grades and Success by Study Visit – Observed Data (Supplemental Analysis) Categorical Results |
| 14.2.2.5 | ITT | Body Investigator Global Assessment (B-IGA) Grades and Success by Study Visit – Non-responder Imputation (Sensitivity Analysis) Categorical Results |
| 14.2.2.6 | ITT | Body Investigator Global Assessment (B-IGA) Grades and Success at Week 8 – Tipping Point Analysis (Sensitivity Analysis) Categorical Results |
| 14.2.2.7 | ITT | Body Investigator Global Assessment (B-IGA) Grades and Success by Study Visit – Multiple Imputation, without Site Stratification (Sensitivity Analysis) Categorical Results |
| 14.2.2.8.1 | ITT | Body Investigator Global Assessment (B-IGA) Success at Week 8 – Multiple Imputation, Impact of Site (Supporting Analysis) |
| 14.2.2.8.2 | ITT | Body Investigator Global Assessment (B-IGA) Success at Week 8 by Site – Observed Data (Supporting Analysis) |
| 14.2.2.9.1 | ITT | Body Investigator Global Assessment (B-IGA) Grades and Success by Study Visit and Response to Topical Corticosteroids – Multiple Imputation (Subgroup Analysis) |
| 14.2.2.9.2 | ITT | Body Investigator Global Assessment (B-IGA) Grades and Success by Study Visit by Study Visit and Age Group – Multiple Imputation (Subgroup Analysis) |
| 14.2.2.9.3 | ITT | Body Investigator Global Assessment (B-IGA) Grades and Success by Study Visit and Baseline S-IGA Disease Severity – Multiple Imputation (Subgroup Analysis) |
| 14.2.2.9.4 | ITT | Body Investigator Global Assessment (B-IGA) Grades and Success by Study Visit and Baseline B-IGA Disease Severity – Multiple Imputation (Subgroup Analysis) |
| 14.2.2.9.5 | ITT | Body Investigator Global Assessment (B-IGA) Grades and Success by Study Visit and Gender – Multiple Imputation (Subgroup Analysis) |
| 14.2.2.9.6 | ITT | Body Investigator Global Assessment (B-IGA) Grades and Success by Study Visit and Ethnicity – Multiple Imputation (Subgroup Analysis) |
| 14.2.2.9.7 | ITT | Body Investigator Global Assessment (B-IGA) Grades and Success by Study Visit and Race – Multiple Imputation (Subgroup Analysis) |
| 14.2.2.9.8 | ITT | Body Investigator Global Assessment (B-IGA) Grades and Success by Study Visit and Fitzpatrick Score – Multiple Imputation (Subgroup Analysis) |
| 14.2.2.9.9 | ITT | Body Investigator Global Assessment (B-IGA) Grades and Success by Study Visit and Facial Involvement – Multiple Imputation (Subgroup Analysis) |
| 14.2.2.9.10 | ITT | Body Investigator Global Assessment (B-IGA) Grades and Success by Study Visit and Genitalia Involvement – Multiple Imputation (Subgroup Analysis) |
| 14.2.2.9.11 | ITT | Body Investigator Global Assessment (B-IGA) Grades and Success by Study Visit and Knee Involvement – Multiple Imputation (Subgroup Analysis) |
| 14.2.2.9.12 | ITT | Body Investigator Global Assessment (B-IGA) Grades and Success by Study Visit and Elbow Involvement – Multiple Imputation (Subgroup Analysis) |

| | | |
|-------------|-----------|---|
| 14.2.2.9.13 | ITT | Body Investigator Global Assessment (B-IGA) Grades and Success by Study Visit and Knee or Elbow Involvement – Multiple Imputation (Subgroup Analysis) |
| 14.2.2.9.14 | ITT | Body Investigator Global Assessment (B-IGA) Grades and Success by Study Visit and Response to Topical Vitamin D Derivatives – Multiple Imputation (Subgroup Analysis) |
| 14.2.2.10 | ITT | Summary, Change, and Percent Change from Baseline in Body Investigator Global Assessment (B-IGA) by Study Visit – Observed Data |
| | | |
| | | |
| 14.2.3.1 | SPRU4-ITT | Average Weekly Scalp Itch–Numeric Rating Scale (SI-NRS) Success by Study Visit – Multiple Imputation (Primary Analysis) |
| 14.2.3.1.s | SPRU4-ITT | Average Weekly Scalp Itch–Numeric Rating Scale (SI-NRS) Success by Study Visit – Multiple Imputation (Primary Analysis, Supplemental Estimand) |
| 14.2.3.2 | SPRU4-ITT | Average Weekly Scalp Itch–Numeric Rating Scale (SI-NRS) Success by Study Visit – Observed Data (Sensitivity Analysis) |
| 14.2.3.3 | SPRU4-ITT | Average Weekly Scalp Itch–Numeric Rating Scale (SI-NRS) Success by Study Visit - Non-responder Imputation (Sensitivity Analysis) |
| 14.2.3.4 | ITT | Average Weekly Scalp Itch–Numeric Rating Scale (SI-NRS) by Study Visit – Multiple Imputation (ANCOVA) |
| 14.2.3.5 | ITT | Summary, Change, and Percent Change of Average Weekly Scalp Itch–Numeric Rating Scale (SI-NRS) by Study Visit – Multiple Imputation |
| 14.2.3.6 | ITT | Average Weekly Scalp Itch–Numeric Rating Scale (SI-NRS) by Study Visit – Observed Data (ANCOVA) |
| 14.2.3.7 | ITT | Summary, Change, and Percent Change of Average Weekly Scalp Itch–Numeric Rating Scale (SI-NRS) by Study Visit – Observed Data |
| 14.2.3.8 | ITT | Daily Scalp Itch–Numeric Rating Scale (SI-NRS) for Day 1 (24-hour) and 72-hour Endpoints – Multiple Imputation (ANCOVA) |
| 14.2.3.9 | ITT | Summary, Change, and Percent Change of Daily Scalp Itch–Numeric Rating Scale (SI-NRS) by Study Day – Multiple Imputation |
| 14.2.4.1 | PRU4-ITT | Average Weekly Worst Itch–Numeric Rating Scale (WI-NRS) Success by Study Visit – Multiple Imputation (Primary Analysis) |
| 14.2.4.1.s | PRU4-ITT | Average Weekly Worst Itch–Numeric Rating Scale (WI-NRS) Success by Study Visit – Multiple Imputation (Primary Analysis, Supplemental Estimand) |
| 14.2.4.2 | PRU4-ITT | Average Weekly Worst Itch–Numeric Rating Scale (WI-NRS) Success by Study Visit – Observed Data (Sensitivity Analysis) |
| 14.2.4.3 | PRU4-ITT | Average Weekly Worst Itch–Numeric Rating Scale (WI-NRS) Success by Study Visit - Non-responder Imputation (Sensitivity Analysis) |
| 14.2.4.4 | ITT | Summary, Change, and Percent Change of Average Weekly Worst Itch–Numeric Rating Scale (WI-NRS) by Study Visit – Observed Data |
| 14.2.4.5 | ITT | Summary, Change, and Percent Change of Daily Worst Itch–Numeric Rating Scale (WI-NRS) by Study Day – Observed Data |
| 14.2.4.6 | ITT | Average Weekly Worst Itch–Numeric Rating Scale (WI-NRS) by Study Visit– Observed Data (ANCOVA) |
| 14.2.4.7 | ITT | Daily Worst Itch–Numeric Rating Scale (WI-NRS) by Study Day – Observed Data (ANCOVA) |
| 14.2.5.1 | ITT | Achievement of Psoriasis Area and Severity Index (PASI-75, PASI-90, PASI-50, PASI-100) by Study Visit – Visit–Multiple Imputation |
| 14.2.5.2 | ITT | Achievement of Psoriasis Area and Severity Index (PASI-75, PASI-90, PASI-50) by Study Visit – Observed Data |

| | | |
|--------------|---|--|
| 14.2.5.3 | ITT | Achievement of Psoriasis Area and Severity Index (PASI-75, PASI-90, PASI-50) by Study Visit – Non-responder Imputation (Sensitivity Analysis) Categorical Results |
| 14.2.5.4 | ITT | Summary of Psoriasis Area and Severity Index (PASI) by Study Visit – Multiple Imputation (ANCOVA) |
| 14.2.5.5 | ITT | Summary, Change and Percent Change from Baseline in Psoriasis Area and Severity Index (PASI) by Study Visit - Multiple Imputation |
| 14.2.5.6 | ITT | Summary of Psoriasis Area and Severity Index (PASI) by Study Visit – Observed Data (ANCOVA) |
| 14.2.5.7 | ITT | Summary, Change and Percent Change from Baseline in Psoriasis Area and Severity Index (PASI) by Study Visit – Observed Data |
| 14.2.6.1 | ITT | Achievement of Psoriasis Scalp Severity Index (PSSI-75, PSSI-50, PSSI-90, PSSI-100) by Study Visit – Multiple Imputation |
| 14.2.6.1.s | ITT | Achievement of Psoriasis Scalp Severity Index (PSSI-75, PSSI-50, PSSI-90, PSSI-100) by Study Visit – Multiple Imputation (Secondary Analysis, Supplemental Estimand) |
| 14.2.6.2 | ITT | Achievement of Psoriasis Scalp Severity Index (PSSI-75, PSSI-50, PSSI-90, PSSI-100) by Study Visit – Observed Data |
| 14.2.6.3 | ITT | Achievement of Psoriasis Scalp Severity Index (PSSI-75, PSSI-90, PSSI-50, PSSI-100) by Study Visit – Non-responder Imputation (Sensitivity Analysis) Categorical Results |
| 14.2.6.4 | ITT | Summary of Psoriasis Scalp Severity Index (PSSI) by Study Visit – Multiple Imputation (ANCOVA) |
| 14.2.6.5 | ITT | Summary, Change and Percent Change from Baseline in Psoriasis Scalp Severity Index (PSSI) by Study Visit - Multiple Imputation |
| 14.2.6.6 | ITT | Summary of Psoriasis Scalp Severity Index (PSSI) by Study Visit – Observed Data (ANCOVA) |
| 14.2.6.7 | ITT | Summary, Change and Percent Change from Baseline in Psoriasis Scalp Severity Index (PSSI) by Study Visit – Observed Data |
| 14.2.7.1.1 | ITT - Patients with Age ≥ 18 years | Summary of Psoriasis Symptoms Diary (PSD) Aggregate Score of Itching/Pain/Scaling by Study Visit – Multiple Imputation (ANCOVA) |
| 14.2.7.1.1.s | ITT - Patients with Age ≥ 18 years | Summary of Psoriasis Symptoms Diary (PSD) Aggregate Score of Itching/Pain/Scaling by Study Visit – Multiple Imputation (ANCOVA) (Secondary Analysis, Supplemental Estimand) |
| 14.2.7.1.2 | ITT - Patients with Age ≥ 18 years | Summary, Change, and Percent Change from Baseline in Psoriasis Symptoms Diary (PSD) Aggregate Score of Itching/Pain/Scaling by Study Visit – Multiple Imputation |
| 14.2.7.1.3 | ITT - Patients with Age ≥ 18 years | Summary of Psoriasis Symptoms Diary (PSD) Aggregate Score of Itching/Pain/Scaling by Study Visit – Observed Data (ANCOVA) |
| 14.2.7.1.4 | ITT - Patients with Age ≥ 18 years | Summary, Change, and Percent Change from Baseline in Psoriasis Symptoms Diary (PSD) Aggregate Score of Itching/Pain/Scaling by Study Visit – Observed Data |
| 14.2.7.2.1 | ITT - Patients with Age ≥ 18 years | Achievement of Score of 0 for Psoriasis Symptoms Diary (PSD) Item Related to Scaling by Study Visit – Multiple Imputation |
| 14.2.7.2.1.s | ITT - Patients with Age ≥ 18 years | Achievement of Score of 0 for Psoriasis Symptoms Diary (PSD) Item Related to Scaling by Study Visit – Multiple Imputation (Secondary Analysis, Supplemental Estimand) |
| 14.2.7.2.2 | ITT - Patients with Age ≥ 18 years | Achievement of Score of 0 for Psoriasis Symptoms Diary (PSD) Item Related to Scaling by Study Visit – Observed Data (Sensitivity Analysis) |

| | | |
|--------------|---|--|
| 14.2.7.2.3 | ITT - Patients with Age ≥ 18 years | Achievement of Score of 0 for Psoriasis Symptoms Diary (PSD) Item Related to Scaling by Study Visit – Non-responder Imputation (Sensitivity Analysis) |
| 14.2.7.3.1 | ITT - Patients with Age ≥ 18 years | Achievement of Score of 0 for Psoriasis Symptoms Diary (PSD) Item Related to Itching by Study Visit – Multiple Imputation |
| 14.2.7.3.1.s | ITT - Patients with Age ≥ 18 years | Achievement of Score of 0 for Psoriasis Symptoms Diary (PSD) Item Related to Itching by Study Visit – Multiple Imputation (Secondary Analysis, Supplemental Estimand) |
| 14.2.7.3.2 | ITT - Patients with Age ≥ 18 years | Achievement of Score of 0 for Psoriasis Symptoms Diary (PSD) Item Related to Itching by Study Visit – Observed Data (Sensitivity Analysis) |
| 14.2.7.3.3 | ITT - Patients with Age ≥ 18 years | Achievement of Score of 0 for Psoriasis Symptoms Diary (PSD) Item Related to Itching by Study Visit – Non-responder Imputation (Sensitivity Analysis) |
| 14.2.7.4.1 | ITT - Patients with Age ≥ 18 years | Achievement of Score of 0 for Psoriasis Symptoms Diary (PSD) Item Related to Pain by Study Visit – Multiple Imputation |
| 14.2.7.4.1.s | ITT - Patients with Age ≥ 18 years | Achievement of Score of 0 for Psoriasis Symptoms Diary (PSD) Item Related to Pain by Study Visit – Multiple Imputation (Secondary Analysis, Supplemental Estimand) |
| 14.2.7.4.2 | ITT - Patients with Age ≥ 18 years | Achievement of Score of 0 for Psoriasis Symptoms Diary (PSD) Item Related to Pain by Study Visit – Observed Data (Sensitivity Analysis) |
| 14.2.7.4.3 | ITT - Patients with Age ≥ 18 years | Achievement of Score of 0 for Psoriasis Symptoms Diary (PSD) Item Related to Pain by Study Visit – Non-responder Imputation (Sensitivity Analysis) |
| 14.2.7.5.1 | ITT - Patients with Age ≥ 18 years | Achievement of Score of 0 for Psoriasis Symptoms Diary (PSD) Total Score by Study Visit – Multiple Imputation |
| 14.2.7.5.1.s | ITT - Patients with Age ≥ 18 years | Achievement of Score of 0 for Psoriasis Symptoms Diary (PSD) Total Score by Study Visit – Multiple Imputation (Secondary Analysis, Supplemental Estimand) |
| 14.2.7.5.2 | ITT - Patients with Age ≥ 18 years | Achievement of Score of 0 for Psoriasis Symptoms Diary (PSD) Total Score by Study Visit – Observed Data (Sensitivity Analysis) |
| 14.2.7.5.3 | ITT - Patients with Age ≥ 18 years | Achievement of Score of 0 for Psoriasis Symptoms Diary (PSD) Total Score by Study Visit – Non-responder Imputation (Sensitivity Analysis) |
| 14.2.7.6.1 | ITT - Patients with Age ≥ 18 years | Summary of Psoriasis Symptoms Diary (PSD) by Study Visit – Multiple Imputation (ANCOVA) |
| 14.2.7.6.2 | ITT - Patients with Age ≥ 18 years | Summary, Change and Percent Change from Baseline in Psoriasis Symptoms Diary (PSD) by Study Visit – Multiple Imputation |
| 14.2.7.6.3 | ITT - Patients with Age ≥ 18 years | Summary of Psoriasis Symptoms Diary (PSD) by Study Visit – Observed Data (ANCOVA) |
